14.4 Timing of Collection of Data Elements

Scan data will be transferred to the cooperating labs for analysis within a month of the scan date. All other data will be transcribed from the clinical records within a month of the last protocol-related treatment/examination.

14.5 Data Storage and Protection

Non-image data will be maintained in a web-based REDCap database developed specifically for this study. The REDCap database is password-protected. The PI will grant permission for specific study staff to have access to the portion of data pertinent to their role on the study.

Imaging data will be securely transferred to the [name] and [name] laboratories, where they will be stored in a password protected data archive housed behind the Partner's firewall. The MRI data to be transferred will be coded with the subject's study ID and not by name, to ensure confidentiality.

14.6 Data and Safety Monitoring

The DF/HCC Data and Safety Monitoring Committee (DSMC) will review and monitor toxicity and accrual data from this trial. The committee is composed of clinical specialists with experience in oncology and who have no direct relationship with the study. Information that raises any questions about participant safety will be addressed with the Principal Investigator and study team.

The DSMC will meet annually and/or more often if required to review toxicity and accrual data. Information to be provided to the committee may include: up-to-date participant accrual; all grade 2 or higher unexpected adverse events that have been reported; audit results, and a summary provided by the study team. Other information (e.g. scans, laboratory values) will be provided upon request.

15. STATISTICAL CONSIDERATIONS

15.1 Study Design/Endpoints

The primary objective of this study is to determine the feasibility of utilizing pulmonary DCE-MRI to assess changes from baseline in tumor perfusion during SBRT treatment

CONFIDENTIAL

This document is confidential. Do not disclose or use except as authorized.

(after 1 fraction of SBRT), and 1-2 weeks and 3-4 months after completion of SBRT treatment for stage I NSCLC. **Feasibility (success) is defined as successfully enrolling patients, processing the pulmonary DCE-MRI data, and observing an analyzable change in tumor perfusion between the pre-treatment DCE-MRI and any of the DCE-MRI scans during SBRT (after 1 fraction) or after completion of SBRT treatment. Analyzable change will be defined as a 20% change in tumor perfusion. A recent publication by Ng et al reported the rate of reproducibility of DCE-MRI parameters was between 10-20% (Ng, Raunig et al. 2010), and we have chosen the upper limit of this range to be conservative.**

A total of 20 participants with stage I NSCLC will be enrolled on this study, and a two-stage design will be used. Seven eligible participants in the first stage and 10 eligible participants in the second stage will be accrued. To allow for participants that are unable to complete scans and/or are ineligible to continue on the study, 3 additional participants will be accrued, so up to 8 participants in stage I and 12 participants in stage II will be accrued to this study. If at least 5 successes are observed among the 7 eligible participants in the first stage, up to an additional 12 participants (10 eligible) will be entered. If 14 or more successes are observed among the 17 eligible participants, utilizing pulmonary DCE-MRI to assess changes in tumor perfusion will be considered feasible for this group. With this design, there is a 90% probability of declaring the pilot study feasible if the true feasibility rate is 90%, and a 10% probability of declaring the DCE-MRI worthy of further study if the true feasibility rate is 65%. With 17 eligible participants, we have 90% power to detect a difference of 0.75 standard deviation in the change of tumor perfusion from baseline (prior to SBRT treatment) to post treatment (either right after SBRT treatment or 3-4 months after SBRT treatment) using a 0.1 level two-sided Wilcoxon signed-rank test.

After stage I accrual is met, the pulmonary DCE-MRI data will be reviewed. If the changes in tumor perfusion could only be observed in one or two of the scans during and after treatment compared to the pre-SBRT scan, patients enrolled in the 2nd stage won't be required to undergo all three during and after treatment pulmonary DCE-MRIs and only the time points with useful information will be obtained to save resources.

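### Section 15.1 fixes the three replacement places as one in stage I and two in stage II, with no way to move a place and no rule for fewer than 7 eligible participants at the stage I look; pooling the places would cost almost nothing

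*Combined protocol and SAP*

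**What the plan says.** Section 15.1 sets the stage sizes: "Seven eligible participants in the first stage and 10 eligible participants in the second stage will be accrued". The overall number is also fixed: "A total of 20 participants with stage I NSCLC will be enrolled on this study". The difference between 17 and 20 is a cushion, introduced with "To allow for participants that are unable to complete scans and/or are ineligible to continue on the study", and it is then allotted by stage: "3 additional participants will be accrued, so up to 8 participants in stage I and 12 participants in stage II will be accrued". The stage II cap is repeated as "up to an additional 12 participants (10 eligible) will be entered".

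Both decision rules assume the quotas are met. The stage I rule begins "If at least 5 successes are observed among the 7 eligible participants in the first stage" and the final rule begins "If 14 or more successes are observed among the 17 eligible participants". For this design 15.1 states a 90% chance of declaring feasibility at a true rate of 90%, and a 10% chance at a true rate of 65%.

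No section gives an expected loss rate, allows an unused place to pass from one stage to the other, or says what happens if stage I closes with fewer than 7 eligible. Section 6.1 places the look after 7 eligible participants without repeating the cap of 8. It also describes the full enrolment of 20 as eligible, where 15.1 has 17 eligible out of 20.

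**The concern.** If two of the first eight participants are lost, stage I has 6 eligible and the written cap keeps a ninth out, although total accrual would still be within 20. The two spare places reserved for stage II cannot be used where they are needed. In the other direction, an unused stage I place cannot cover a third loss in stage II.

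The study team would then have to take the go/no-go on fewer than 7, under a rule worded only for 7, or change the plan at the interim. If the threshold of 5 successes is kept, a shortfall raises the chance of stopping a method that is in fact feasible. The stated 90% and 10% hold only if 7 and then 17 are reached. Section 15.2 expects about 6 participants a year, so a wrong or disputed stop would be slow to repair.

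**Working it through.** **Inputs, all from 15.1:** quotas of 7 and 10 eligible; caps of 8 and 12; thresholds of 5 among 7 and 14 among 17; true rates of 0.90 and 0.65. The loss rate d is an assumption, so it is shown over a range.

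**1. The plan's own figures.** P(declare feasible) = Σ over x = 5, 6, 7 of P(X₁ = x | 7, p) × P(X₂ ≥ 14 − x | 10, p).
- p = 0.90: 0.1240 × 0.7361 + 0.3720 × 0.9298 + 0.4783 × 0.9872 = 0.909.
- p = 0.65: 0.2985 × 0.0860 + 0.1848 × 0.2616 + 0.0490 × 0.5138 = 0.099.

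Both agree with the stated 90% and 10%. At p = 0.90 with a full 7, the chance of stopping at stage I is 2.6%.

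**2. What the cushion implies.** Three places in 20 is 15%, and 17/0.85 = 20 exactly. At the same rate stage I would need 7/0.85 = 8.24, so 9, which is above its cap of 8. Stage II would need 10/0.85 = 11.8, so 12, which is its cap. Stage I's own cushion is 1 in 8, or 12.5%.

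**3. Stage I shortfall.** P(fewer than 7 of 8) = 1 − (1 − d)⁸ − 8d(1 − d)⁷. At d = 0.15 this is 1 − 0.2725 − 0.3847 = 0.343. As a check, if exactly 3 of the 20 are lost at random, the chance that at least 2 fall among the first 8 is 0.344. If stage I could draw on all three spares (10 places), the shortfall at 15% would be 5.0%.

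**4. Filling both quotas at 15% loss.** Split: (1 − 0.343) × (1 − 0.264) = 0.484. Pooled: P(at least 17 of 20) = 0.648.

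**5. Effect on the decisions.** Assume p = 0.90 among eligible participants, the thresholds of 5 and 14 kept, and unfilled places counted as non-successes. For the split at 15% loss, stage I ends with 7 (probability 0.6572), 6 (0.2376), 5 (0.0839) or fewer than 5 (0.0214). The matching chances of fewer than 5 successes are 0.0257, 0.1143, 0.4095 and 1. The wrong-stop probability is

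0.6572 × 0.0257 + 0.2376 × 0.1143 + 0.0839 × 0.4095 + 0.0214 = 0.100.

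With pooled places (accrue until 7 eligible or 10 accrued, then until 17 eligible or 20 accrued) it is 0.034. Carrying both schemes through to the final rule by exact enumeration gives:

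| Loss rate d | Stage I below 7 (cap 8) | Declared feasible, split | Declared feasible, pooled |
|---|---|---|---|
| 5% | 5.7% | 89.5% | 90.7% |
| 10% | 18.7% | 84.3% | 87.9% |
| 12.5% | 26.4% | 80.0% | 84.6% |
| 15% | 34.3% | 74.5% | 79.9% |
| 20% | 49.7% | 60.7% | 66.6% |

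At a true rate of 65%, the same enumeration for pooled places gives 9.8%, 9.1% and 7.4% at losses of 5%, 10% and 15%. Pooling therefore does not push the false-positive rate above the stated 10%.

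**The case against.** **The loss rate.** A reader might infer that the plan itself expects 15% loss. It does not say so; 15% is the size of the cushion, and stage I's own 1 in 8 gives 26% rather than 34%. The documents also point to lower loss. Success under 15.1 needs a change on any one of the follow-up scans. Section 15.5.2 keeps everyone with a baseline scan and at least one post-treatment scan. Section 13.4 skips a scan for low renal function and re-tests at the next time point. Section 5.1 cancels registrations with no protocol therapy, and whether these use up a place is not stated. At 5% loss pooling gains about one percentage point. This objection stands, and it is why the result has to be given as a range.

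**The consequence.** A reader might also infer that in a third of trials the stage I decision could not be taken, or that the trial would stop. Neither follows. With 6 eligible, 5 or 6 successes already meet the threshold, and 3 or fewer could not have met it even with a seventh participant; only 4 of 6 is open. Counting all shortfalls at a true rate of 90%, the outcome depends on the missing participants in 7.8% of trials at 15% loss, 3.3% at 10% and 0.8% at 5%. This also stands.

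**Attribution.** The wrong-stop and declaration figures rest on scoring unfilled places as non-successes, which no section states. Most of the fall from 90.9% to 74.5% at 15% loss is ordinary loss that pooling does not cure; the split accounts for about 5 points.

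**Flexibility.** Section 6.1 does not repeat the cap of 8, and 16.1 allows amendments approved by the ethics board, so a ninth stage I participant has a route. That route is a change made at the interim, which a sentence written now would avoid.

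**Conclusion.** The point holds as a cheap improvement to a stated rule. The split leaves stage I with a single spare, no means of borrowing another, and no rule for fewer than 7. The chance of falling short is 6% to 50% over assumed losses of 5% to 20%, and 26% to 34% at the two rates that the plan's own cushions suggest.

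The cost to the decision is smaller than the shortfall figures. With independent losses, a true rate of 90% and unfilled places counted as non-successes, pooling raises the chance of declaring feasibility by 1.2 points at 5% loss, 3.6 at 10% and 5.4 at 15%. At 15% it cuts the wrong stage I stop from 10.0% to 3.4%. Pooling fills both quotas whenever the split does. It does not restore 90% power at 15% loss. The documents do not support saying that the plan assumes 15% loss, or that a shortfall stops the trial.

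**What to change.** Replace the sentence in 15.1 that allots the spare places with: *Up to 3 additional participants in total may be accrued, in either stage, until 7 and then 17 eligible participants (as defined in 15.5.2) are reached; total accrual will not exceed 20.* Keep the 5-of-7 and 14-of-17 cut-offs. The reference to 15.5.2 is deliberate: it keeps the plan's word, eligible, and ties it to the existing inclusion rule for the primary endpoint, so that it is clear who is replaced and who is counted.

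Pooling makes a stage I shortfall rare but not impossible (5.0% at 15% loss), so one clause on how the stage I threshold applies below 7 would close the remaining gap.

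The maximum enrolment does not change. The cost is that up to 10 participants, two more than now, may enter before the stage I look, which could leave no spares for stage II. In the same edit, reconcile 6.1, which describes 20 eligible participants, with the 17 eligible of 20 accrued in 15.1.

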15.2 Sample Size/Accrual Rate

Twenty participants will be enrolled in this pilot study. We estimate that approximately 20 patients a year would meet the eligibility criteria for enrollment on this study. Assuming that one third of the eligible patients would consent to enrolling on the study, the accrual rate would be 6 patients per year and accrual will be complete within 3.5 years. After the last post-treatment DCE-MRI scan (3-4 months after treatment), participants will be off study, but will continue to undergo follow-up per standard care. Thus, the study will be complete after 4 years.

15.3 Stratification Factors

CONFIDENTIAL

This document is confidential. Do not disclose or use except as authorized.

None

15.4 Analysis of Secondary Endpoints

Secondary endpoints include the feasibility of pulmonary DCE-MRI in characterizing acute and subacute radiation-induced lung injury after SBRT as well as the feasibility of using pulmonary DCE-MRI to identify regions of functional lung for SBRT treatment planning. The feasibility rates of these two endpoints will be calculated along with a 95% confidence interval based on the binomial distribution, and the confidence interval will be no wider than 50%.

- 15.4.1 To evaluate the feasibility of pulmonary DCE-MRI in characterizing acute (1-2 weeks) and subacute (3 months) radiation-induced lung injury after SBRT, and correlate these findings with clinical outcomes. **Feasibility (success) is defined as successfully enrolling patients, processing the pulmonary DCE-MRI data, and observing an analyzable change in lung perfusion on the 3-month scan.**
- 15.4.2 To evaluate the feasibility of integrating 4D-CT ventilation imaging with DCE-MRI perfusion imaging in characterizing subacute (3 months) radiation-induced lung injury after SBRT. **Feasibility (success) is defined as successfully enrolling patients, processing the pulmonary DCE-MRI and 4D-CT data, and observing an analyzable change on the 3-month scan.**
- 15.4.3 To determine the feasibility of using pulmonary DCE-MRI to identify regions of functional lung for planning SBRT for peripheral lung tumors. **Feasibility will be defined as the ability to perform a retrospective comparative treatment planning study using the DCE-MRI images acquired prior to treatment for each participant.** Regions of functional and non-functional lung will be defined on each MRI, and the images will be registered to the 4DCT used for treatment planning. The functional-lung contours will be transferred to the 4D-CT based on this registration. The target volume and other critical structures will be defined as per standard treatment protocol, as described in Section 6 of this document. In addition to the normal-tissue constraints outlined in Section 6, the treatment plan will attempt to maximize sparing of functional-lung regions while maintaining adequate target coverage and not exceeding other normal-tissue constraints. The functional-lung based treatment plans generated in this manner will be compared to the corresponding standard plans that were used to treat the patient. Changes in the functional-lung V20 and V5 will be used to analyze changes in functional-lung sparing.

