15.5 Reporting and Exclusions

- 15.5.1 **Evaluation of toxicity.** All participants will be evaluable for toxicity from the time of their first DCE MRI.
- 15.5.2 **Evaluation of primary endpoint.** All participants who undergo a pre-treatment DCE-MRI and at least one post-treatment DCE-MRI will be included in the study.

CONFIDENTIAL

This document is confidential. Do not disclose or use except as authorized.

15.5.3 **Stopping Rules.** There is no experimental component to the radiation treatment or radiological imaging (both SBRT and the DCE-MRI are utilized in routine clinical care). However, the study will be stopped if preliminary study results determine that it is not feasible to utilize DCE-MRI to achieve any of the primary or secondary objectives including assessing tumor perfusion (primary objective) and lung injury or assisting SBRT treatment planning.

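### Section 15.4 promises an interval no wider than 50% without condition, but the exact interval guarantees this only with 17 or more contributing participants, and a stage I stop or a dropped 3-month scan would leave 7 or 8

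*Combined protocol and SAP*

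**What the plan says.** Section 15.4 gives two secondary feasibility rates, one for characterizing lung injury and one for identifying functional lung for planning. Each is to be reported with a "95% confidence interval based on the binomial distribution", and the section adds that "the confidence interval will be no wider than 50" percent. It states no sample size, denominator or handling of missing scans. Success for lung injury (15.4.1) and for the 4D-CT integration (15.4.2) is defined on the 3-month scan. The planning endpoint (15.4.3) uses the pre-treatment scan.

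The sample size is in Section 15.1: "Seven eligible participants in the first stage and 10 eligible participants in the second stage will be accrued". To cover incomplete scans and ineligibility, "3 additional participants will be accrued, so up to 8 participants in stage I and 12 participants in stage II" may be entered. Stage II opens only if at least 5 of the first 7 succeed. The same section says: "With 17 eligible participants, we have 90% power to detect a difference of 0.75 standard deviation", "using a 0.1 level two-sided Wilcoxon signed-rank test".

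The last paragraph of Section 15.1 provides for a data review after stage I. If tumor perfusion changes show on only one or two of the later scans, stage II patients "won't be required to undergo all three during and after treatment pulmonary DCE-MRIs", and only the informative time points are kept. Section 13.4 separately lets a single scan be missed for low renal function while the participant stays on study.

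**The concern.** The width statement reads as a property of the design whatever happens, yet it depends on how many participants supply the scan in question. Two of the plan's own rules can bring that number far below 17. The more serious is the scan-dropping rule. It looks only at tumor perfusion, the primary endpoint, whereas the scan it may remove also carries two secondary endpoints that concern lung rather than tumor. Followed as written, it could leave 15.4.1 and 15.4.2 with stage I data only, and leave the lung-injury rate reported with much less precision than promised. Nothing in the plan acknowledges this.

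**Working it through.** **Inputs.** Confidence level 95%, binomial, bound 50 points (Section 15.4). Eligible participants 7 + 10 = 17; enrolled up to 8 + 12 = 20; stage II opens at 5 or more successes in 7; design rates 65% and 90%; signed-rank test at two-sided 0.10 for 0.75 SD (Section 15.1). The interval is read as exact (Clopper-Pearson), since the plan names no other.

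**Formula.** For x successes in n, the lower limit is the 0.025 quantile of Beta(x, n − x + 1) and the upper limit is the 0.975 quantile of Beta(x + 1, n − x). The width is upper minus lower. A promise made before the data must hold at the x that gives the greatest width.

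**The plan's figure reproduces at 17.** At x = 8 the limits are 23.0% and 72.2%, so the width is 49.2%, the maximum over all x. The bound is met, with 0.8 points to spare.

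**Fewer contributing.**

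| n | x at maximum | 95% limits | Maximum width |
|---|---|---|---|
| 17 | 8 or 9 | 23.0% to 72.2% (x = 8) | 49.2% |
| 16 | 8 | 24.7% to 75.4% | 50.7% |
| 14 | 7 | 23.0% to 77.0% | 53.9% |
| 8 | 4 | 15.7% to 84.3% | 68.6% |
| 7 | 3 or 4 | 9.9% to 81.6% (x = 3) | 71.7% |

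So 17 is the smallest n that guarantees the bound. At 16 the excess is at most 0.7 points and arises only for 7 to 9 successes. At 7 or 8 the width exceeds 50% at every count except none or all: 6 of 7 gives 57.5% and 7 of 8 gives 52.3%.

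**Case 1: stop after stage I.** The chance of fewer than 5 successes in 7 at a true rate of 65% is 1 − (0.2985 + 0.1848 + 0.0490) = 0.468, or 47%. At 90% it is 1 − (0.1240 + 0.3720 + 0.4783) = 0.026. A stop leaves 7 eligible participants for both promised rates, including planning, with no scan missing.

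**Case 2: 3-month scan dropped for stage II.** Only the 7 or 8 stage I participants could have it, so the maximum width for lung injury is 69% to 72%. The 4D-CT endpoint loses the same participants. The planning endpoint is not affected, because it uses the pre-treatment scan.

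**Scattered missing scans.** The documents give no miss rate. If scans were missed independently at an assumed 5%, 10% or 15%, the chance that at least 17 of 20 have a given scan would be 98%, 87% or 65%.

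**Signed-rank power.** With exact critical values and normally distributed changes, simulated power at 0.75 SD is 89.2% for 17 pairs, against the stated 90%; a paired t-test gives 90.5%. The figure therefore reproduces. It is 81.5% at 14, 53.5% at 8 and 47.6% at 7.

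**The case against.** Much can be said for the plan, and most of it stands.

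- **The buffer.** Up to 20 participants are accrued to yield 17, so it would be wrong to infer that a single missing 3-month scan breaks the promise. Near 17 the shortfall is trivial in any case.
- **The power.** A reader might infer that the 90% power is overstated. It is not: the sentence is tied to 17 participants and reproduces. Dropping one time point does not reduce the number at a retained one. The figure simply does not apply to a time point that fewer than 17 have.
- **Scope.** A reader might extend the width promise to the 4D-CT endpoint. Section 15.4 makes it for lung injury and planning only. Nor does the rule in 15.5.2, which asks for a baseline scan and "at least one post-treatment DCE-MRI", set the secondary denominator; it is headed as governing the primary endpoint.
- **Choice of interval and denominator.** Other intervals keep within 50% at smaller n: Wald to 16, Jeffreys to 13, Wilson to 12. Wilson still reaches 59.1% at 7 and 57.0% at 8. Counting a missed scan as a failure among 17 would preserve the bound, but the plan does not say this, and it would make no sense for a scan omitted by design.
- **Likelihood.** Nobody expects final-sample precision after a stage I stop, and the prostate data cited in Section 1.2 (a 40% fall at 2 months, 75% at 6) suggest that the late scan is a less likely one to be dropped. No go/no-go decision rests on the interval width.

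The last point lowers the probability of the second case but does not remove the conflict: the dropping rule ignores endpoints that need the scan, and the width is promised without condition.

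**Conclusion.** The concern holds in a limited form. The 50% bound is correct for 17 or more contributing participants and is not guaranteed below that. The failure is material in two situations: a stage I stop (up to 71.7% for both promised rates, with a 47% chance of stopping if the true feasibility rate is 65%), and removal of the 3-month scan from stage II (69% to 72% for lung injury, with 15.4.2 also confined to stage I participants). This rests on the exact interval and on a denominator of participants who have the scan; the documents fix neither explicitly. The primary two-stage rule and the power statement are not in question.

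**What to change.** 1. In Section 15.4, make the bound conditional, for example: no wider than 50% if at least 17 participants contribute, and up to 54% with 14 or 72% with 7 (exact interval). Name the interval, and state the denominator and how a missing scan is counted.
2. Reconcile the last paragraph of Section 15.1 with 15.4.1 and 15.4.2. Either base the decision to drop a time point on the lung-injury and 4D-CT endpoints as well as on tumor perfusion, or state that, if the 3-month scan is dropped, those endpoints will be assessed in stage I participants only, with the wider interval.

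The first change costs only a less favourable stated figure. The second may give up part of the resource saving if it leads to the 3-month scan being retained; that scan is already scheduled, so it adds no procedure. No change to the sample size, the two-stage rule or the power figure is needed.
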